4.2 Important Subgroups

Each dose cohort will be summarized as an independent subgroup. Other subgroups may be defined as needed.

5 ENDPOINTS AND COVARIATES

5.1 Efficacy Endpoints

Response will be categorized as complete response (CR), partial response (PR), stable disease (SD), or progressive disease (PD) and evaluated using RECIST 1.1 criteria and as immune-related complete response (irCR), immune-related partial response (irPR), immune-related stable disease (irSD), or immune-related progressive disease (irPD) using irRC. The ORR will be the proportion of patients in the response evaluable population achieving CR or PR when such responses are confirmed at least 28 days after the initial observation of an objective response. A two-sided 95% exact binomial confidence interval will be calculated around the ORR for each expansion cohort.

Duration of response (DoR) will be calculated for responders as the time from initial response (CR or PR) to the time of PD or death, whichever occurs first. Kaplan-Meier methods will be used to estimate DoR over time and the median DoR. Responders who complete the study without documented PD will be censored at the date of their last tumor assessment.

PFS and irPFS will be calculated as the time from the initial infusion of pembrolizumab or MGA271 until documented disease progression, or death from any cause. Patients with no PFS event (disease progression or death from any cause) will be censored at the date of their last tumor assessment. In addition, PFS and irPFS rates will be calculated at 3-month and 6-month year time points from the first dose of study drug. Kaplan-Meier methods will be used to estimate PFS over time and the median duration of PFS. The method of Brookmeyer and Crowley (1) will be used to construct 95% CIs around PFS estimates of the median and other quartiles for each expansion cohort.

Incomplete and missing data can complicate interpretation of PFS. **Table 3** describes the handling of these data for the PFS analysis.

Overall survival (OS) is defined as the time from the initial infusion of pembrolizumab or MGA271 to death from any cause. Kaplan-Meier methods will be used to estimate the overall survival function. Patients who do not die will be censored at the date that the patient was last known to be alive. In addition, OS will be calculated at 6 months from the first dose of study drug.

Table 3 Censoring Rules for PFS Analysis

Situation	Date	Outcome
No baseline tumor assessments	Date of 1 st dose	Censored
Death prior to the 1 st scheduled tumor assessment	Date of death	Progressed
No post-baseline tumor assessments in absence of death	Date of 1 st dose	Censored

Situation	Date	Outcome
prior to the 1 st scheduled tumor assessment		
Documented disease progression	Date of disease progression	Progressed
Initiation of alternative anti-cancer treatments in absence of disease progression	Date of last tumor assessment prior to initiation of such treatment	Censored
Death or disease progression immediately after missing two or more consecutive scheduled tumor assessments	Date of last tumor assessment prior to missed assessments	Censored

5.2 Safety Endpoints

5.2.1 Adverse Events

Adverse event (AE) means any untoward medical occurrence in a patient or clinical trial patient associated with the use of a drug in humans, whether or not considered drug related. An adverse event can therefore be any unfavorable and unintended sign (including an abnormal laboratory finding, for example), symptom, or disease temporally associated with the use of a medicinal product, whether or not considered related to the medicinal product. Only treatment emergent adverse events (TEAEs) will be summarized as safety endpoints. A TEAE is defined as any event that is newly occurring on or after the administration of study drug or an event that existed before but increased in severity on or after study drug administration.

All adverse events whether serious or non-serious, will be reported from the time a signed and dated ICF is obtained through the end of treatment visit (EOTV) or 28 days following the last dose of study (whichever occurs later). These events will be recorded by the Investigators in the electronic case report forms (eCRFs). AEs will be coded using the most recent version of the Medical Dictionary for Regulatory Activities (MedDRA). An assessment of severity grade will be made using National Cancer Institute- Common Terminology Criteria for Adverse Events (NCI-CTCAE) Version 4.03.

Both protocol-related AEs and serious adverse events (SAEs) will be collected from the time the patient has consented to study participation. AEs and SAEs reported between the time the patient signs the ICF and the administration of the first dose of study drug will be captured as concurrent medical history unless the events are attributed to protocol-specified procedures. Events attributed to protocol-specified procedures will be collected on the Adverse Event eCRFs and SAE Report form as appropriate.

5.2.2 Laboratory Values

Safety laboratory assessments will be carried out locally and evaluated by the Investigator to ensure patient safety. If the Investigator determines the laboratory value is an abnormal change from baseline and is of clinical significance for that patient, it is considered an AE. Generally, Grade 1 laboratory findings need not be reported as AEs unless clinically significant. The Investigator will evaluate laboratory findings of \geq Grade 2 or higher classification to determine their clinical significance and if an AE has occurred. Consistent with the CTCAE designation of Grade 3 events as severe or medically significant and Grade 4 events as life-threatening, Grade 3 and Grade 4 laboratory findings should be reported as AEs or SAEs, as appropriate. Grade 2 laboratory findings may be reported as AEs if, in the opinion of the Investigator, the event exhibits clinical significance. If clinically relevant abnormal laboratory values are associated with clinical symptom(s), or consistent with a diagnosis, the diagnosis should be reported as the AE (e.g., hemoglobin 9 g/dL in an adult female = anemia). If these clinically relevant abnormal laboratory values do not result in a diagnosis, the test result or finding should be reported as the AE assuming that it does not represent a laboratory error. Such laboratory values should generally be recorded as “increased” or “decreased” (e.g., change from baseline hemoglobin of 13 g/dL to 11 g/dL = hemoglobin decreased).

5.2.3 Other Safety Endpoints

Physical examination will be performed (including weight and height) for all patients according to the schedules outlined in the protocol.

Vital signs (include temperature, pulse, blood pressure, and respiratory rate) and Eastern Cooperative Oncology Group (ECOG) performance status will be performed according to the schedules outlined in the protocol.

Twelve-lead electrocardiograms (ECGs) will be obtained according to the protocol to evaluate the potential cardiac effects of the combination of MGA271 and pembrolizumab and of MGA271+MGA012, including QT interval. To account for intrinsic variability, all ECGs should be obtained in triplicate (3 ECGs per time point at approximately 1-minute intervals). Central interpretation will be used for data analysis purposes. For Cohort 4 only, ECGs will be read locally.

5.3 Pharmacokinetic, Pharmacodynamic, and Immunological Parameter Endpoints

Central laboratories will be used to measure serum concentrations (for PK evaluations), cytokines, T-cell repertoire, anti-drug antibodies (ADA, anti-MGA271 and anti-MGA012 antibodies) as well as the other pharmacodynamic parameters. The timepoints for collection of blood samples for each of these tests are included in the study protocol.

6 STATISTICAL METHODOLOGY

6.1 General Considerations

Summary statistics will consist of absolute and relative frequencies of each category of discrete variables and of means, standard deviations, medians, minimum and maximum values for continuous variables. Categorical data will be summarized by the number and percent of subjects falling within each category. Continuous variables will be summarized by descriptive statistics, including the mean, standard deviation, median, minimum, and maximum. Time-to-event endpoints will be summarized with median durations and corresponding 95% confidence intervals.

For change from baseline calculations, baseline is defined as the most recent value prior to the first infusion of any of the study drugs among MGA271, pembrolizumab or MGA012.

6.2 Missing Data

Data reported as missing will be treated as missing in all data summaries. Imputation rules for partially recorded dates, where complete dates are required to carry out an analysis, will be provided in the statistical programming plan (SPP). In descriptive summaries for safety, observations that are spurious (extreme relative to the majority of the data) will not be altered or removed from the summary.

6.3 Patient Disposition and Baseline Characteristics

6.3.1 Patient Disposition

For patient disposition, the number and percentage of patients who reach various study milestones are summarized in each patient category. All screened patients are categorized into two groups: patients with screen failures (with reasons if collected) and enrolled. Then the enrolled patient group is further categorized into two subgroups: never treated (with reasons if collected) and treated with any of the study drugs. The “treated with any study drugs” category will further be divided into the treatment ongoing (if any) and treatment discontinuation (with reasons for discontinuation, which also include protocol-defined treatment completion, if any) categories. The end of study status for all enrolled patients will also be included.

6.3.2 Patient Demographics and Baseline Characteristics

Patient demographics, baseline characteristics, disease history, medical history, prior cancer therapy, and other collected baseline data will be summarized using descriptive statistics.

6.4 Study Drug Exposure and Concomitant Medications

Study drug exposure and concomitant medications will be summarized by descriptive statistics. The summary of study drug exposure will include descriptive statistics as well as frequency counts for the number of doses or cycles received, the total dose actually administrated as well as the total dose intended, and the dose intensity, which is calculated as percentage of total dose actually administrated divided by total dose intended during the treatment period.

Duration of study treatment (months) will be calculated as:

(date decided to discontinue treatment – date of first dose + 1)/(365.25/12) for patients who have discontinued treatment.

The summary of concomitant medications will include the number and percentage of patients who receive any concomitant medications as well as each concomitant medication by World Health Organization Anatomical Therapeutic Chemical (ATC) first level and Preferred Term (PT).

6.5 Protocol Deviations

Major protocol deviations will be documented and filed prior to database lock. The major protocol deviations will be listed and summarized in the final analysis.

6.6 Efficacy Endpoint Analyses

6.6.1 Objective Response

Objective response rate (ORR), determined by RECIST and irRC criteria, will be calculated by [REDACTED] tumor type and will be based on a confirmed response at least 28 days after initial observation of response. Two-sided 95% exact binomial confidence intervals (CIs) will be calculated around the ORRs. [REDACTED]
[REDACTED]
[REDACTED]

[REDACTED] For SCCHN and NSCLC, ORR from participants with or without prior PD-1/PD-L1 treatments will be summarized in separate tumor type groups. [REDACTED]
[REDACTED]
[REDACTED]

Objective responses that are not subsequently documented with a confirmed response by CT or MRI scan (e.g. unconfirmed responses) will not be included as an objective response for the purpose of calculating overall objective response rates. Response rate will be calculated as:

Objective response rate (ORR) = number of patients with confirmed response (CR or PR) / number of patients with response evaluable

6.6.2 Tumor Size Change from Baseline

The tumor size percent change from baseline over time will be summarized and presented by spider plot. The best tumor size percent change from baseline prior to the date of first PD or initiation of new anticancer therapy will be presented by waterfall plot. Patients with CR or PR at time of last assessment will be censored at the time of their last tumor assessment. Using statistical notation, if y_t denotes the sum of the measurements at some post-baseline timepoint and y_0 denotes the sum of the measurements at baseline, the percent change from baseline will be calculated as:

$$(y_t - y_0) / y_0 \times 100$$

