All other lesions (or sites of disease) including pathological lymph nodes should be identified as *non-target lesions* and should also be recorded at baseline. Measurements are not required and these lesions should be followed as 'present', 'absent', or in rare cases 'unequivocal progression. In addition, it is possible to record multiple non-target lesions involving the same organ as a single item on the case record form (e.g. 'multiple enlarged pelvic lymph nodes' or 'multiple liver metastases').

RESPONSE CRITERIA

This section provides the definitions of the criteria used to determine objective tumor response for target lesions.

Evaluation of target lesions

Complete Response (CR): Disappearance of all target lesions. Any pathological lymph nodes (whether target or non-target) must have reduction in short axis to < 10 mm.

Partial Response (PR): at least a 30% decrease in the sum of diameters of target lesions, taking as reference the baseline sum diameters.

Progressive Disease (PD): at least a 20% increase in the sum of diameters of target lesions, taking as reference the *smallest sum on study* (this includes the baseline sum if that is the smallest on study). In addition to the relative increase of 20%, the sum must also demonstrate an absolute increase of at least 5 mm. (*Note*: the appearance of one or more new lesions is also considered progression).

Stable Disease (SD): Neither sufficient shrinkage to qualify for PR nor sufficient increase to qualify for PD, taking as reference the smallest sum diameters while on study.

Special notes on the assessment of target lesions

Lymph nodes. Lymph nodes identified as target lesions should always have the actual short axis measurement recorded (measured in the same anatomical plane as the baseline examination), even if the nodes regress to below 10 mm on study. This means that when lymph nodes are included as target lesions, the ‘sum’ of lesions may not be zero even if complete response criteria are met, since a normal lymph node is defined as having a short axis of <10 mm. In order to qualify for CR, each node must achieve a short axis <10 mm. For PR, SD and PD, the actual short axis measurement of the nodes is to be included in the sum of target lesions.

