3.1 Overall Study Design and Plan

3.1.1 General Study Design

This study is a Phase 1, open-label, dose escalation, and cohort expansion study designed to characterize the safety, tolerability, PK, PD, immunogenicity, and preliminary antitumor activity of MGA271 administered IV weekly in combination with pembrolizumab administered IV Q3W. Beginning with Amendment 5, this study also characterizes the safety and tolerability of MGA271 administered IV Q3W in combination with MGA012, both administered IV Q3W (cohort 4).

This study consists of a Dose Escalation Phase to determine the MTD or MAD (if no MTD is determined) of MGA271 administered in combination with 2 mg/kg pembrolizumab, followed by a Cohort Expansion Phase to further define the safety and initial efficacy of the combination with the MGA271 dose established in the first phase. The study treatment schema is presented in **Figure 1**.

Figure 1 MGA271 + Pembrolizumab Treatment Schema

a Patients may receive up to 5 subsequent 9-week treatment cycles of MGA271 + pembrolizumab depending on response to study treatments

* All patients will enter an Efficacy Follow-up Period after receipt of the last dose of study treatment to be followed for up to 24 weeks for survival.

[figure not shown]
MGA271 will be administered as an IV infusion over 120 minutes on a once-weekly schedule. Pembrolizumab will be administered at 2 mg/kg as an IV infusion over 30 minutes Q3W. On the days that both agents are administered, pembrolizumab will be administered first, followed by MGA271.

For both the Dose Escalation and Cohort Expansion phases, the first tumor assessment will be obtained on Cycle 1 Study Day 42 of the Initial Tumor Assessment Cycle.

Patients who remain clinically stable and do not experience unacceptable toxicity that necessitates permanent discontinuation of the study drugs, at the completion of the Initial (6-week) Tumor Assessment Cycle will be eligible to receive additional treatment with pembrolizumab and MGA271. Assuming that the patient remains clinically stable, maintains a response status of SD or better, and does not experience unacceptable toxicity that necessitates permanent discontinuation of the study drugs, patients may receive up to 5 additional 9-week treatment cycles during Subsequent Tumor Assessment Cycles, for a maximum total of 51 doses of MGA271 and 17 doses of pembrolizumab.

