4 STUDY POPULATIONS AND SUBGROUPS

4.1 Study populations

Two populations will be used for analysis, the Safety Population and the Response Evaluable Population, as defined below:

- **Safety Population:** All patients who received at least one dose of MGA271, pembrolizumab or MGA012. Safety Population will be used to summarize baseline data, safety data and for assessment of overall survival (OS) and progression-free survival (PFS). Patients who receive at least one dose of MGA271 or MGA012 will be included in PK, PD, and immunogenicity analyses.
- **Response Evaluable Population:** All patients who received MGA271 and pembrolizumab, or MGA271 and MGA012, and had at least 1 post-infusion radiographic tumor assessments. Patients who meet these criteria will be eligible for the determination of best overall response and will be included in the response evaluable population used for the calculation of objective response rates (ORRs) using both conventional RECIST 1.1 and irRC criteria.

Patients who withdraw before receiving all protocol-specified treatment before completion of the DLT evaluation period, for a reason unrelated to drug toxicity will be considered to have inadequate data to support dose escalation. In this case, replacement patients may be enrolled at the same dose level and schedule as necessary to complete the cohort.

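### Read as written, the waterfall rule in SAP 6.6.2 leaves no bar for a patient with PD at the first scan, so nearly all bars at or above +20% are lost

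*SAP*

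**What the plan says.** SAP 6.6.2 plans two displays of tumor size. The spider plot shows percent change over time, with no stated cut-off. The waterfall plot shows one value per patient: "The best tumor size percent change from baseline prior to the date of first PD or initiation of new anticancer therapy". The percent change is computed from a quantity that "denotes the sum of the measurements at some post-baseline timepoint", relative to the baseline sum.

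On timing, SAP 3.1.1 states that "the first tumor assessment will be obtained on Cycle 1 Study Day 42". On who is evaluable, SAP 4.1 requires that the patient received the combination and "had at least 1 post-infusion radiographic tumor assessments". SAP 6.6.1 uses that population as the ORR denominator.

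SAP 6.6.2 also contains this sentence: "Patients with CR or PR at time of last assessment will be censored at the time of their last tumor assessment". The same sentence stands in the DoR paragraph of SAP 6.6.3.

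SAP 6.6.2 does not say which patients the waterfall plot covers, what to do when no value is eligible, or whether PD means RECIST 1.1 PD or irPD.

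**The concern.** The date of PD is the date of the scan that shows it, and a scan on that date does not precede it. If the first post-baseline scan shows PD, nothing measured after baseline falls inside the window. Baseline itself (0%) cannot stand in, because the formula takes post-baseline sums only.

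The missing bars would not be a random subset. They belong to patients who progressed at the first look, among them those whose target lesions grew most. Preliminary antitumor activity is a secondary objective. A reader who takes the waterfall plot as a picture of all evaluable patients would see too little growth and too large a share of shrinkage. The figure would also rest on a different set of patients from the ORR, without saying so.

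**Working it through.** The documents give no planned figure for this plot, so there is none to reproduce. The check applies the rule and then illustrates its size.

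**Inputs**
- Window, formula and stray sentence: SAP 6.6.2.
- First scan at Day 42: SAP 3.1.1.
- PD by target growth, Protocol Appendix 5: "at least a 20% increase in the sum of diameters of target lesions", measured from the smallest sum on study, plus an absolute increase of at least 5 mm. At the first scan the smallest earlier sum is baseline.
- PD by new lesion, Protocol Appendix 5: "the appearance of one or more new lesions is also considered progression".
- Response rates, Protocol 2.3.1.1.2, Table 1: SCCHN 33.3% of 18, NSCLC 35.7% of 14.
- Share with PD at the first scan: not in the documents. Assumed range 10% to 40%.

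**Step 1: eligible values for a patient with PD at Day 42.** Scheduled post-baseline scans before Day 42: 0. Eligible values: 0. Bars: 0. The same patient has one post-infusion scan and so stays in the ORR denominator.

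**Step 2: which bars are lost.** The plotted value is the lowest eligible change. For it to be +20% or more, the first scan must itself be at +20% or more. That is PD unless the absolute growth is under 5 mm, which needs a baseline sum below 5 / 0.20 = 25 mm. Apart from that exception, no bar at or above +20% can appear, whatever the true PD rate.

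**Step 3: illustrative size.** The responder counts are 18 × 0.333 ≈ 6 (6/18 = 33.3%) and 14 × 0.357 ≈ 5 (5/14 = 35.7%), matching Table 1. With n patients, r responders and an assumed share p with first-scan PD, k = n × p (rounded) bars are lost and the responder share of bars is r / (n − k). This treats the Table 1 N as the evaluable number and keeps every responder's bar.

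| p | SCCHN, n = 18, r = 6 | NSCLC, n = 14, r = 5 |
|---|---|---|
| none dropped | 6/18 = 33.3% | 5/14 = 35.7% |
| 10% | 6/16 = 37.5% | 5/13 = 38.5% |
| 20% | 6/14 = 42.9% | 5/11 = 45.5% |
| 30% | 6/13 = 46.2% | 5/10 = 50.0% |
| 40% | 6/11 = 54.5% | 5/8 = 62.5% |

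**Step 4: net direction.** A patient with PD from a new lesion alone may have shrinking targets, and losing that bar makes the plot look worse. A toy simulation weighed the two effects. It assumed two scans, a first-scan change with SD 30 points and mean 0 or +10, a second-scan increment with SD 20, and new-lesion PD in 10% regardless of target change; it ignored the 5 mm condition. Among first-scan progressors, 15.5% (mean 0) and 8.5% (mean +10) had shrinking targets. Moving from a window that includes the PD scan to the literal rule shifted the median best change from −6% to −18% and from +5% to −13%. The net shift was favourable in both settings.

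**The case against.** The strongest reply is that this is loose wording rather than a decision to omit patients. SAP 6.6.2 does not say that anyone is left out, and SAP section 7 sends figure shells and programming detail to a separate programming plan that is not among the documents. That plan may handle the case. This limits what can be said about the figure that will be produced. It does not cure the rule, since section 7 describes the outputs as based on the analyses in the SAP, and a programmer who follows 6.6.2 exactly produces the truncated plot.

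A second reply is that stopping at first PD is sound. That stands. The rule drops the PD scan and every later one, and Protocol 7.11.1.1 allows treatment beyond conventional PD because some tumors respond afterwards. So the cut-off also discards some favourable late values. Only the loss of the PD scan itself is at fault.

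A third reply is that the effect stays inside one descriptive figure. That also stands. The ORR keeps its own denominator and exact interval, no decision rule in the documents uses the waterfall plot, and the spider plot can still show early growth.

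**Conclusion.** The concern holds as a defect in one display rule. As written, SAP 6.6.2 leaves first-scan progressors without a bar and cuts off almost all of the plot at or above +20%. That part follows from the documents alone. The size does not: with an assumed 10% to 40% having PD at Day 42, the responder share of bars rises from 33.3% to between 37.5% and 54.5% for SCCHN, and from 35.7% to between 38.5% and 62.5% for NSCLC.

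A reader might infer more than the documents support:
- **That the reported response rate is inflated.** It is not. ORR counts these patients, and DoR, PFS and OS do not use this rule.
- **That every lost bar is unfavourable.** New-lesion PD with shrinking targets is an exception. How many such patients are affected depends on the PD criterion, because under Protocol Appendix 6 a new lesion alone is not irPD.
- **That responders would fill two thirds of the bars.** That needs half of the SCCHN patients to progress by Day 42 (6/9 = 67%), and nothing in the documents supports such a rate.

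The repeated censoring sentence changes no value. A best percent change cannot be censored, so the sentence is an editorial carry-over.

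**What to change.** In SAP 6.6.2:

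1. Define the waterfall value as the best (lowest) percent change from baseline among post-baseline assessments on or before the date of first PD and before any new anticancer therapy. Scans after first PD stay excluded.
2. Name the criterion: RECIST 1.1 PD for the main plot, and irPD for any version under irRC.
3. Plot every response evaluable patient with a measured post-baseline target sum. Add a footnote with the number evaluable but not plotted, and the reasons.
4. Delete the censoring sentence as an editorial correction.

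The programming plan should carry the same wording. The cost is a few words and no new data. The downside for the sponsor is that the plot will look slightly less favourable.
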